2.4 Endpoints

The primary endpoint on this study is defined as completion of all study drug over the first 4 weeks of study treatment (initial and crossover treatment phases).

Secondary endpoints include number of bowel movements per week, as captured on the Patient bowel movement diary (**Appendix F**), stool quality as measured by the Bristol Stool Scale (**Appendix G**), safety defined as the rate of drug-related adverse events experienced assessed according to the NCI's CTCAE v4.03 toxicity criteria, and health related quality of life and pain measures as assessed by the PAC-SYM, PAC-QOL, and BPI-sf, within the first 4 weeks of study treatment (see **section 9.3.3**).

Exploratory endpoints will include drug administration compliance as measured by weekly pill counts by a member of the study team, healthcare resource utilization as defined by the number of number of emergency room visits, hospitalizations, telephone encounters, and EPIC mychart

encounters related to signs and symptoms of constipation, and patient preference (yes/no) for naloxegol to treat OIC as defined by choice of participation in the optional extension phase of the study.

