4.2 Treatment Administration

Patients in Arm A will receive a single daily dose of 25mg naloxegol for the 2-week initial treatment period, followed by a 3-day washout period and 2-week crossover treatment period in which the patient will receive the treating physician's usual care for OIC using a stimulant laxative ± rescue medication.

Patients in Arm B will receive the treating physician's usual care for OIC using a stimulant laxative ± rescue medication for the 2-week initial treatment period, followed by a 3-day washout period and 2-week crossover period in which the patient will receive a single daily dose of 25mg naloxegol.

Patients on Arms A and B will have the option to continue on naloxegol at 25 mg daily for an additional 12-week extension phase upon completion of initial and crossover treatment phases.

Patients will be instructed to take naloxegol on an empty stomach at least 1 hour prior to the first meal of the day or 2 hours after the meal. Tablets must be swallowed whole, and not crushed or chewed by the subject. Subjects will also be instructed to avoid consumption of grapefruit or grapefruit juice as this is a potent inhibitor of the CYP3A4 enzyme.

Patients will also be instructed to complete a daily study drug diary during the treatment phases when naloxegol is being administered. Patients will be asked to bring their completed study drug diary with them during each visit for review with a member of the study team.

If the patient misses their daily morning dose of naloxegol and it has been less than 2 hours since the missed dose, they will be instructed to take naloxegol as soon as it is remembered on the same day. If it has been more than 2 hours since missing a dose, the patient will be instructed to skip the dose for that day not to make up that dose. If the patient vomits after taking a dose, he/she will be instructed not to repeat the dose or attempt to make up that dose.

If a patient takes more than the assigned daily dose of naloxegol, they should be monitored closely for evidence of opioid withdrawal symptoms and reversal of central analgesic effects. In cases of known or suspected overdose, symptomatic treatment as well as monitoring of vital functions should be performed. In cases of severe intoxication, intensive care procedures are recommended. Close medical supervision and monitoring should be continued until the patient recovers.

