5.1.13.1 Patient Study Drug Diary

Patients will complete a daily study drug diary (**Appendix D**) during the period of time that they are receiving naloxegol: initial treatment phase for patients randomized to Arm A, crossover treatment phase for those randomized to Arm B; extension phase for all patients who choose to continue receiving naloxegol for an additional 12 weeks following the crossover phase. Participants will be asked to complete this diary even on days when a naloxegol dose was missed. The study drug diary will be reviewed with the patient during each visit to clinic, and a copy will be collected by a member of the study team. This diary will be used in combination with a pill count by the study team to support drug accountability.

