9.3.4 Exploratory Endpoints

Exploratory aims include laxative compliance (weekly pill counts), healthcare resource utilization (per electronic medical record evaluation of emergency room visits, hospitalizations, telephone encounters, and Mychart encounters), and patient preference (as evidenced by patient desire to continue naloxegol optional 12-week extension).

For analysis of differences in weekly pill counts between naloxegol and usual care, we plan to use a Poisson generalized linear mixed effects model to determine the impact of naloxegol on weekly pill counts, over the course of 2 weeks for the initial treatment and cross over phases of the study.

Count of healthcare utilization resource- will be the sum of total utilizations (summed separately for each of the two weeks for initial treatment and cross over phase). Differences in healthcare utilization between the arms will be determined by fitting a Poisson regression model (or negative binomial in the case of over dispersion) of treatment arm on bi-weekly utilization count. We will examine patient preference by calculating a 95% confidence interval for the proportion

of patients who wish to continue the optional 12-week extension.

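### Preference for naloxegol is defined as entering a naloxegol-only extension open only to completers, and is summarised as one proportion with no stated denominator and no split by sequence

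*Combined protocol and SAP*

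**What the plan says.** Section 2.4 (Endpoints) defines the exploratory endpoint as "patient preference (yes/no) for naloxegol to treat OIC as defined by choice of participation in the optional extension phase". Section 9.3.4 (Exploratory Endpoints) gives the whole analysis: "We will examine patient preference by calculating a 95% confidence interval for the proportion" "of patients who wish to continue the optional 12-week extension". It has no arm term, no by-arm display and no comparison with usual care, and it does not say which patients form the denominator.

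Section 4.2 (Treatment Administration) lets both arms go on to an "additional 12-week extension phase upon completion of initial and crossover treatment phases". Section 5.1.13.1 describes this phase as the "extension phase for all patients who choose to continue receiving naloxegol for an additional 12 weeks following the crossover phase", and the regimen table in section 4.1 shows naloxegol as its only treatment in both arms. Section 8.1 says the drug is supplied free of charge.

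The arms reach the choice from different treatments. In section 4.2, Arm A's naloxegol period is "followed by a 3-day washout period and 2-week crossover treatment period in which the patient will receive the treating" physician's usual care; Arm B has the reverse order and ends on naloxegol.

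For the primary endpoint, section 9.2 keeps dropouts in the analytic sample as non-completers. No such rule is given for preference.

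**The concern.** There are three separate problems.

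1. **Who is counted.** A patient who stops early, for example for an adverse event or after failed rescue (sections 4.4 and 4.7), is not offered the extension. If the denominator is those who were offered it, the proportion describes only patients who got through both phases. Because the denominator is not fixed, it could be chosen after the data are seen.
2. **What is hidden.** Arm A chooses at about Day 32, after 14 days of usual care, with its last scheduled naloxegol dose on Day 14. Arm B chooses directly after naloxegol. The word continue fits Arm B but not Arm A. One pooled figure conceals any effect of order, although the randomised sequences would show it at no extra cost. Section 9.3.3 already allows for a period effect in the secondary models.
3. **What a yes means.** The alternative to entering is leaving the study, not taking usual care within it. Free drug may raise uptake; further visits, diaries and pill counts may lower it. No question asks patients to compare the two treatments.

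Sections 2.4 and 9.3.4 also differ on what is counted: the first uses the choice to participate, the second the wish or desire to continue. At stake is whether the trial can report a preference finding at all, or only an uptake figure.

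**Working it through.** **Inputs from the documents.** 50 patients commence study treatment; acceptable completion rate 70%; assumed true rate 85%; one-sided exact binomial test at 0.05 (section 9.2); 1:1 allocation (section 10.3). No uptake rate, sample size or precision is given for preference, so every entry count below is an assumption.

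**The plan's own figure.** For n = 50, the smallest r with P(X ≥ r | 0.70) ≤ 0.05 is 41: the exact alpha is 0.0402 at 41 and 0.0789 at 40. Power is P(X ≥ 41 | 0.85) = 0.791, so the stated 80% reproduces.

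**Completion scenarios.** 35 completers (70% of 50), 41 (the pass mark) and 43 (about 85%).

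**Ratio of the two figures.** With x entrants and c completers, (x/c) ÷ (x/50) = 50/c, whatever x is.
- c = 43: 50/43 = 1.16
- c = 41: 50/41 = 1.22
- c = 35: 50/35 = 1.43

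**Gap in percentage points, assuming 40% to 80% of completers enter (x rounded).**
- c = 43: 17/43 − 17/50 = 39.5 − 34.0 = 5.5; 34/43 − 34/50 = 79.1 − 68.0 = 11.1
- c = 41: 16/41 − 16/50 = 39.0 − 32.0 = 7.0; 33/41 − 33/50 = 80.5 − 66.0 = 14.5
- c = 35: 14/35 − 14/50 = 40.0 − 28.0 = 12.0; 28/35 − 28/50 = 80.0 − 56.0 = 24.0

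**When the denominator changes the reading against 50%.** The plan sets no threshold; 50% is used here because it is where a reader would start to speak of a majority. Exact (Clopper-Pearson) 95% intervals at 41 completers:

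| Entrants | Of 41 completers | Of 50 treated |
|---|---|---|
| 27 | 65.9% (49.4 to 79.9) | 54.0% (39.3 to 68.2) |
| 28 | 68.3% (51.9 to 81.9) | 56.0% (41.3 to 70.0) |
| 29 | 70.7% (54.5 to 83.9) | 58.0% (43.2 to 71.8) |
| 32 | 78.0% (62.4 to 89.4) | 64.0% (49.2 to 77.1) |
| 33 | 80.5% (65.1 to 91.2) | 66.0% (51.2 to 78.8) |

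The lower limit is above 50% on one denominator and not the other only for 28 to 32 entrants. The corresponding ranges are 29 to 32 at 43 completers and 24 to 32 at 35.

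**Pooling.** Suppose uptake among completers is 40% in Arm A and 80% in Arm B.
- 21 and 21 completers: (0.4 × 21 + 0.8 × 21)/42 = 60.0%, the simple mean
- 24 and 18: (9.6 + 14.4)/42 = 57.1%
- 18 and 24: (7.2 + 19.2)/42 = 62.9%

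Pooling can move the estimate either way and has no built-in upward push. A 40-point difference between sequences would nevertheless be invisible in the single figure.

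**Precision by sequence.** With about 21 completers per arm, 13/21 = 61.9% (38.4 to 81.9).

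**The case against.** A reader might infer that the planned analysis inflates preference. The documents do not support that as a fact. Section 9.3.4 says only patients; if all 50 treated are the denominator there is no inflation, and pooling 1:1 sequences averages an order effect. Free supply and visit burden act in opposite directions, so the net bias as a measure of preference is unknown. This objection stands.

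It may also be said that the label is open about itself. Section 2.3 speaks of preference to continue naloxegol in the extension, section 2.4 states the definition, and neither claims preference over usual care or plans a majority claim. That is fair, and it limits the criticism to what may be concluded. It does not remove it: section 2.4 still names a preference for naloxegol as OIC treatment, which entry into a one-treatment extension cannot show.

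The all-treated denominator has its own weakness. It counts as no an Arm B patient who left during usual care without ever taking naloxegol, and a patient who stopped because of unrelated illness. This also stands, and is why reasons for stopping belong beside the figure.

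Finally, 41 is the pass mark for the primary endpoint, which is completion of all study drug (section 2.4) or all procedures (section 9.3.1). A patient who missed doses might fail that endpoint yet finish both phases and be offered the extension. The number offered the extension may therefore exceed the number of primary-endpoint completers, and the ratios would then be smaller.

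**Conclusion.** The concern holds in a limited form. As written, the endpoint measures uptake of a free, naloxegol-only extension among patients who finish both phases, and it cannot support a conclusion about preference between naloxegol and usual care. The denominator is unstated. If completers are used, the figure is 1.16 to 1.43 times the all-treated figure over 43 down to 35 completers, and the excess grows as completion worsens. The factor of 1.22 belongs to 41 completers only.

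Whether the denominator changes the reading against 50% depends on entry numbers that the documents do not give. At 41 completers it does so for 28 to 32 entrants and for no other number. Pooling hides an order effect but does not inflate the estimate. These figures assume 50 treated patients and that those offered the extension are the same as the completers counted.

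The consequence is modest: the endpoint is exploratory, it has no hypothesis test, and the primary result is unaffected.

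**What to change.** In sections 2.4 and 9.3.4:

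- Name the measure uptake of the naloxegol extension, and make no claim of preference over usual care.
- Use one definition in both sections, either the stated wish or actual entry.
- Take all patients who commenced study treatment as the denominator, with early stoppers counted as not continuing, and show the completers-only figure alongside.
- Report both by randomised sequence and pooled, with exact 95% confidence intervals.
- List early stops by the treatment being taken at the time and by reason, because some will occur on usual care or from unrelated illness.

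The cost is wording and one table; the data are already being collected. The downside is that the all-treated figure is lower and describes uptake rather than pure acceptability, and that the by-sequence intervals will be wide.

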10.0 STUDY MANAGEMENT

10.1 Conflict of Interest

Any investigator who has a conflict of interest with this study (patent ownership, royalties, or financial gain greater than the minimum allowable by their institution, etc.) must have the conflict reviewed according to UCSD conflict of interest policy.

10.2 IRB Approval and Consent

The IRB should approve the consent form and protocol prior to any study-related activities. It is expected that the IRB will have the proper representation and function in accordance with federally mandated regulations.

In obtaining and documenting informed consent, the investigator should comply with the applicable regulatory requirement(s), and should adhere to Good Clinical Practice (GCP) and to ethical principles that have their origin in the Declaration of Helsinki.

Before recruitment and enrollment onto this study, the patient will be given a full explanation of the study and will be given the opportunity to review the consent form. Each consent form must include all the relevant elements currently required by FDA Regulations and local or state regulations. Once this essential information has been provided to the patient and the investigator is assured that the patient understands the implications of participating in the study, the patient will be asked to give consent to participate in the study by signing an IRB-approved consent form.

Prior to a patient's participation in the trial, the written informed consent form should be signed and personally dated by the patient and by the person who conducted the informed consent discussion.

10.3 Registration and Randomization Procedures

All patients must be registered with the UCSD Moores Cancer Center Clinical Trials Office before enrollment to study. Prior to registration, eligibility criteria must be confirmed and an eligibility checklist completed. Once eligibility is confirmed, patient will be given a unique sequential study number.

Patients will be randomized in a 1:1 ratio to either Arm A or Arm B by block randomization within 3 days of the initial study treatment day. Randomization will be performed by CTRI using a randomization package in the software R (blockrand)^{15,16}. The CTRI office will provide the study coordinator with prestuffed envelopes numbered 1-62. In the envelope, a paper will indicate the treatment assignment. One envelope will be assigned to each patient by the study coordinator in order of accrual. The number on the envelope will become the patient number and will be the identification number on all study documents. Individual patient randomization arm must be assigned prior to the patient being treated on study. The study coordinator will contact IDS once subject randomization arm has been confirmed.

10.4 Data Collection and Management

Records and data to be obtained from the study subjects are detailed above in the **Schedule of Events**. Subject outcome information will be documented in the electronic medical record and subject's research record. Data for this study will be entered into a password-protected set of electronic case report forms via the Velos eResearch web-based system. Velos eResearch is an integrated software system for managing clinical trials. This system supports several clinical trial functions, including electronic case report forms, tracking and scheduling of subject visits and events, and study reporting. The software links to the UCSD Health System's EPIC Electronic Medical Record System to provide improved information and integration for clinical research projects. A robust support team assists investigators in implementing protocols and calendars and building electronic case report forms. Velos provides automated data export procedures for designated users into Excel, and then transferred into R. Access to the Velos database for this study will be limited to those users required to perform study-specific functions such as data entry and monitoring. A designated study coordinator from the UCSD Moores Cancer Center Clinical Trials Office will be responsible for entering all study data.

10.5 Subject Data Protection

In accordance with the Health Information Portability and Accountability Act (HIPAA), subjects who have provided written informed consent must also sign a subject authorization to release medical information to the study Sponsor and allow a regulatory authority, or IRB access to subject's medical information relevant to the study.

10.6 Data and Safety Monitoring/Auditing

In addition to AE monitoring and clinical oversight by the principal investigator and co-investigators, quality assurance of the study will be performed by a UCSD Moores Cancer Center Clinical Trials Office internal monitor. Monitoring intervals will be dependent upon the rate of enrollment, and are anticipated to occur approximately every 3-6 months.

This study will also use the UCSD Moores Cancer Center DSMB to provide oversight in the event that this treatment approach leads to unforeseen toxicities. The DSMB will operate according to the DSMB charter. Data from this study will be reported every 6 months and will include:

- 1) the protocol title, IRB protocol number, and the activation date of the study
- 2) the number of patients enrolled to date
- 3) the dates of patient enrollment
- 4) a summary of all adverse events regardless of grade and attribution
- 5) endpoint evaluation for evaluable patients when available
- 6) a summary of any recent literature that may affect the ethics of the study

It will be left to the Investigator's clinical judgment whether or not an AE is related and of sufficient severity to require the subject's removal from treatment. Subsequent review of serious, unexpected and related AEs by the principal investigator, DSMB, UCSD HRPP, and/or AstraZeneca may also result in suspension of further trial interventions/ administration of study drug at a site. The principal investigator or AstraZeneca retains the authority to suspend additional enrollment for the entire study as applicable.

10.7 Adherence to the Protocol

Except for an emergency situation in which proper care for the protection, safety, and well-being of the study patient requires alternative treatment, investigators will conduct their research according to the plans reviewed and approved by the IRB.

10.7.1 Emergency Modifications

Investigators may implement a deviation from, or a change of, the protocol to eliminate apparent immediate hazards/risks to trial subjects without prior IRB approval. Any such emergency modification implemented must be noted and reported to the IRB along the lines of a protocol deviation or violation, depending on the nature of the modification.

10.7.2 Protocol Violations

Any unplanned variance from an IRB approved protocol is considered a violation and must be reported to the IRB in a timely fashion.

A. Major violations must be reported to the IRB within 10 working days of awareness of the violation.

Major violations include:

- Instances that have harmed or increased the risk of harm to one or more research participants.
- Instances that have damaged the scientific integrity of the data collected for the study.
- Results from willful or knowing misconduct on the part of the investigator(s).
- Demonstrates serious or continuing noncompliance with federal regulations, State laws, or University policies.

B. Minor violations may be reported to the IRB at the time of the continuing review. Minor violations have no substantive effect on the risks to participants or on the scientific integrity of the research plan or the value of the data collected.

10.8 Amendments to the Protocol

Should amendments to the protocol be required, the amendments will be originated and documented by the Principal Investigator. It should also be noted that when an amendment to the protocol substantially alters the study design or the potential risk to the patient, a revised consent form might be required.

The written amendment, and if required the amended consent form, must be sent to the UCSD IRB for approval prior to implementation.

10.9 Record Retention

Study documentation includes all case report forms, data correction forms or queries, source documents, Sponsor-Investigator correspondence, monitoring logs/letters, and regulatory documents (e.g., protocol and amendments, IRB correspondence and approval, signed patient consent forms).

Source documents include all recordings of observations or notations of clinical activities and all

reports and records necessary for the evaluation and reconstruction of the clinical research study.

Government agency regulations and directives require that the study investigator must retain all study documentation pertaining to the conduct of a clinical trial. In the case of a study with a drug seeking regulatory approval and marketing, these documents shall be retained for at least two years after the last approval of marketing application in an International Conference on Harmonization (ICH) region. In all other cases, study documents should be kept on file until three years after the completion and final study report of this investigational study.

10.10 Obligations of Investigators

The Principal Investigator is responsible for the conduct of the clinical trial at the site in accordance with Title 21 of the Code of Federal Regulations and/or the Declaration of Helsinki. The Principal Investigator is responsible for personally overseeing the treatment of all study patients. The Principal Investigator must assure that all study site personnel, including sub-investigators and other study staff members, adhere to the study protocol and all FDA/GCP/NCI regulations and guidelines regarding clinical trials both during and after study completion.

The Principal Investigator will be responsible for assuring that all the required data will be collected and entered onto the Case Report Forms. Periodically, monitoring visits will be conducted and the Principal Investigator will provide access to his/her original records to permit verification of proper entry of data. At the completion of the study, all case report forms will be reviewed by the Principal Investigator and will require his/her final signature to verify the accuracy of the data.

